8.2. Detecting and recording adverse events and serious adverse events

8.2.1. Time period for detecting and recording adverse events and serious adverse events

All AEs starting following administration of each dose of study vaccine (Day 0 to Day 30) must be recorded into the appropriate section of the eCRF, irrespective of intensity or whether or not they are considered vaccination-related.

The time period for collecting and recording SAEs will begin at the first receipt of study vaccine and will end 30 days following administration of the last dose of study vaccine for each subject. See Section 8.3 for instructions on reporting of SAEs.

All AEs/SAEs leading to withdrawal from the study will be collected and recorded from the time of the first receipt of study vaccine.

SAEs that are related to the investigational vaccine will be collected and recorded from the time of the first receipt of study vaccine until the subject is discharged from the study.

In addition to the above-mentioned reporting requirements and in order to fulfil international reporting obligations, SAEs that are related to study participation (i.e. protocol-mandated procedures, invasive tests, a change from existing therapy) or are related to a concurrent GSK medication/vaccine will be collected and recorded from the time the subject's parent/*adoptive parent* consents to participate in the study until she/he is discharged from the study.

An overview of the protocol-required reporting periods for AEs and SAEs is given in Table 13.

(Amended 11 October 2016)

Table 13 Reporting periods for adverse events and serious adverse events

Event	Pre-V1*	V1	3 d post-V1	30 d post-V1	V2	3 d post-V2	30 d post-V2	V3	3 d post-V3	30 d post-V3	V4	B	3 d post B	30 d post-B	(Study Conclusion)
Time-point		D0			M1.5			M3			M4	M15			M16
Age of subject	3m	3m			4.5m			6m			7m	18m			19m
Study Visit	Visit 1	Visit 1			Visit 2			Visit 3			Visit 4	Visit 5			Visit 6
Solicited local and general AEs															
Large injection site reactions															
Unsolicited AEs															
AEs/SAEs leading to withdrawal from the study															
SAEs related to the investigational vaccine															
SAEs related to study participation or concurrent GSK medication/vaccine															

* i.e. consent obtained. Pre-V: pre-vaccination; V: vaccination; Post-V: post-vaccination; B: Booster vaccination; d: days; D: Day; m: months; M: Month

Large injection site reactions are defined as swelling with a diameter > 50 mm, noticeable diffuse swelling or noticeable increase of limb circumference after the booster vaccination.

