5.5. Outline of study procedures

The list of study procedures is presented in Table 4.

Table 4 List of study procedures (Amended 11 October 2016)

Age of subjects	3 months	4.5 months	6 months	7 months	18 months	19 months
Epochs	Epoch 001 (Primary epoch)				Epoch 002 (Booster epoch)	
Type of contact	Visit 1	Visit 2	Visit 3	Visit 4	Visit 5	Visit 6
Time-points	Day 0	Month 1.5	Month 3	Month 4	Month 15	Month 16
Sampling time-points				Post-Pri		Post-Boost
Informed consent	●					
Check inclusion/exclusion criteria	●					
Collect demographic data	●					
Medical history, including vaccination history	●					
Physical examination	●					
Record gestational age	●					
Measure/record height and weight	●					
Pre-vaccination body temperature	●	●	●		●	
Check warnings and precautions	○	○	○	○	○	
Check contraindications to subsequent vaccination		○	○	○	○	
Pre-vaccination measurement of limb circumference at site of injection by investigator					●	
Vaccine						
Treatment number allocation	○					
Treatment number allocation with subsequent doses		○	○		○	
Recording of administered treatment number	●	●	●		●	
Vaccine administration	●	●	●		●	
Post- vaccination observation for at least 30 minutes	○	○	○		○	
Laboratory Assays						
Blood sampling for antibody determination (approximately 3.5 ml)				●		●
Safety Assessments						
Record any concomitant medication/vaccination	●	●	●	●	●	●
Record any intercurrent medical conditions		●	●	●	●	●
Distribution of diary cards	●	●	●		●	
Recording of solicited adverse events (AEs) (Days 0-3) by subjects' parent(s)/ adoptive parent(s) in the diary cards	●	●	●		●	
Recording of non-serious adverse events (AEs) (Days 0-30) by subjects' parent(s)/ adoptive parent(s) in the diary cards	●	●	●		●	
Recording of Large injection site reaction					●	
Return of diary cards		○	○	○		○
Diary card transcription by investigator		●	●	●		●
Recording of serious adverse events (SAEs)	●	●	●	●	●	●
Recording of SAEs related to study participation or to a concurrent GSK vaccine	●	●	●	●	●	●
Recording of withdrawal due to AEs	●	●	●	●	●	●
Study Conclusion						●

Note: The double-line border following Month 4 and Month 16 indicate the analyses which will be performed separately on all data (i.e. data that are as clean as possible) obtained up to Month 4 (primary epoch) and Month 16 (booster epoch), respectively.

V = vaccination; Post-Pri = One month after the third dose of primary vaccination course; Post-Boost = One month after booster vaccination; ml = millilitres

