● is used to indicate a study procedure that requires documentation in the individual eCRF.

○ is used to indicate a study procedure that does not require documentation in the individual eCRF.

Refer to Section 8.1.3.1 and 5.6.10 for detailed explanation on the reporting of large injection site reactions

The intervals between study visits are presented in Table 5. These intervals determine each subject's evaluability in the according-to-protocol analyses.

Table 5 Intervals between study visits

Interval	Optimal length of interval ¹	Allowed interval ²
Birth → Visit 1	90 days	90-120 days
Visit 1 → Visit 2	45 days	28-62 days
Visit 2 → Visit 3	45 days	28-62 days
Visit 3 → Visit 4	30 days	21-48 days
Birth → Visit 5	540 days	540-570 days
Visit 5 → Visit 6	30 days	21-48 days

¹ Whenever possible the investigator should arrange study visits within this interval.

² Subjects will not be eligible for inclusion in the analyses of the according-to-protocol (ATP) cohort of immunogenicity for the respective epochs if they make the study visit outside this interval. An interval of 21-48 days between Visit 3 and Visit 4, and between Visit 5 and Visit 6 will be considered for the ATP cohort of immunogenicity for the analysis of respective epochs. Refer Section 10.4 for the definition of the cohorts for analysis.

If a subject returns for the Visit 4 or the Visit 6 blood draw prior to completion of the 31-day safety follow-up period, the subject should continue to record this information in the diary card until 31 days post-vaccination and mail the diary card to the site. The investigator will make an attempt to obtain this information as soon as possible after the 31-day follow-up period if it is not mailed in.

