6.5. Contraindications to subsequent vaccination

The following events constitute absolute contraindications to further administration of *Infanrix-IPV/Hib*. If any of these events occur during the study, the subject must not receive additional doses of vaccine but may continue other study procedures at the discretion of the investigator (see Section 8.4).

- Anaphylaxis following the administration of vaccine.
- Any confirmed or suspected immunosuppressive or immunodeficient condition, including HIV infection.
- Any condition that in the judgment of the investigator would make intramuscular injection unsafe.
- Encephalopathy defined as an acute, severe central nervous system disorder occurring within 7 days following vaccination and generally consisting of major alterations in consciousness, unresponsiveness, generalised or focal seizures that persist more than a few hours, with failure to recover within 24 hours.
- Temperature of $\geq 40.0^{\circ}\text{C}$ (tympanic or axillary temperature) within 48 hours of vaccination, not due to another identifiable cause.
- Collapse or shock-like state (hypotonic-hyporesponsive episode) within 48 hours of vaccination.
- Persistent, inconsolable crying occurring within 48 hours of vaccination and lasting ≥ 3 hours.
- Seizures with or without fever occurring within 3 days of vaccination.

Note: A history of febrile convulsions, a family history of convulsions, a family history of Sudden Infant Death Syndrome or a family history of an AE following DTP vaccination do not constitute contraindications.

The following events constitute contraindications to administration of *Infanrix-IPV/Hib* at that point in time; if any of these events occur at the time scheduled for vaccination, the subject may be vaccinated at a later date, within the time window specified in the protocol (see Section 5.5), or the subject may be withdrawn at the discretion of the investigator (see Section 9.2).

- Acute disease and/or fever at the time of vaccination.
 - Fever is defined as temperature $\geq 37.5^{\circ}\text{C}$ for oral, axillary or tympanic route, or $\geq 38.0^{\circ}\text{C}$ for rectal route. The preferred route for recording temperature in this study will be axillary.

Subjects with a minor illness (such as mild diarrhoea, mild upper respiratory infection) without fever can be administered the vaccine.

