10.2. Secondary endpoints

- Immunogenicity with respect to components of the study vaccine.
 - Anti-diphtheria, anti-tetanus, anti-poliovirus types 1, 2 and 3, and anti-PRP seroprotection status, one month after the booster vaccination.
 - Anti- PT, anti-FHA and anti-PRN antibody seropositivity status one month after the booster vaccination.
 - Anti-diphtheria, anti-tetanus, anti-poliovirus types 1, 2 and 3, anti-PRP, anti-PT, anti-FHA, anti-PRN antibody concentrations or titres, one month after the third dose of primary vaccination and one month after the booster vaccination.
- Solicited local and general symptoms.
 - Occurrence of solicited local/general symptoms during the 4-day (Days 0-3) follow-up period after each primary vaccination dose and following the booster vaccination.
- Unsolicited adverse events.
 - Occurrence of unsolicited symptoms during the 31-day (Days 0-30) follow-up period after each primary vaccination dose and following the booster vaccination.
- Serious adverse events.
 - Occurrence of SAEs from Dose 1 up to study end.

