10.8. Analysis of safety

Analysis of safety relative to the primary epoch will include analysis of safety data collected following administration of the three primary doses of study vaccine. Analysis of safety relative to the booster epoch will include analysis of safety data collected following administration of the booster dose of study vaccine. At this second stage, in

order to avoid missing SAEs that have been reported, an SAE summary table including all the events reported during the entire study period will also be generated.

The analysis will be based on the Total vaccinated cohort for both primary and booster epochs. All analyses are descriptive.

- The overall percentage of subjects/doses with at least one local symptom (solicited or unsolicited), with at least one general symptom (solicited or unsolicited) and with any symptom (solicited or unsolicited) during the 4-day (Days 0-3) solicited follow-up period will be tabulated with exact 95% CI [Clopper, 1934] after each vaccine dose and overall primary doses. The same calculations will be done for symptoms (solicited or unsolicited) rated as grade 3 in intensity, for symptoms (solicited or unsolicited) leading to medical advice and for symptoms (solicited or unsolicited) assessed as causally related to vaccination.
- The overall percentage of subjects/doses and of subjects reporting each individual solicited local and general symptom during the 4-day (Days 0-3) solicited follow-up period will be tabulated after each vaccine dose and overall primary doses, with exact 95% CI [Clopper, 1934] after each vaccine dose and overall primary doses. The same calculations will be done for each individual solicited symptom rated as grade 3 in intensity and for each individual solicited symptom assessed as causally related to vaccination.
- Occurrence of fever will be reported per 0.5°C cumulative increments.

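### For children who stop vaccination but stay in the study, protocol 8.2.1 ends all-cause SAE collection long before the SAE endpoint and Table 4 do

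*Protocol*

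**What the plan says.** Protocol 10.2 and SAP 4.2 give the endpoint as "Occurrence of SAEs from Dose 1 up to study end", with no limit on causality. Table 4 (protocol 5.5) has a row for "Recording of serious adverse events (SAEs" that is marked at Visits 1 to 6. It stands apart from the row for SAEs linked to study participation or a concurrent GSK vaccine. For the second-stage analysis, protocol 10.8 adds that "an SAE summary table including all the events reported during the entire study period will also be generated".

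Protocol 8.2.1 sets the collection rules. The all-cause period starts at the first dose and "will end 30 days following administration of the last dose of study vaccine for each subject". Three narrower streams have no 30-day limit:

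- "SAEs that are related to the investigational vaccine will be collected and recorded from the time of the first receipt of study vaccine until" the child is discharged.
- SAEs related to study participation or to a concurrent GSK product are collected from consent to discharge.
- "All AEs/SAEs leading to withdrawal from the study will be collected and recorded from the time of the first receipt of study vaccine".

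Stopping the vaccine is not the same as leaving the study. Under 6.5, after an absolute contraindication, "the subject must not receive additional doses of vaccine but may continue other study procedures at the discretion of the investigator". Section 9.2.2 says likewise that a child withdrawn from the vaccine may remain for follow-up.

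For the SAE analysis, protocol 10.5 and SAP 6.4.1 keep all vaccinated children in the denominator and treat a child with no report of an event as not having had it.

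**The concern.** The endpoint is tied to the end of the study, and the collection rule is tied to each child's own last dose. The two agree only when the last dose is the Month 15 booster. For a child who stops earlier and keeps attending, 8.2.1 and Table 4 give the site different instructions, and 8.2.1 does not deliver what the endpoint needs.

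What could be lost is a later, new SAE that is judged unrelated and does not lead to withdrawal from the study. How long such events are collected would depend on whether dosing stopped, and dosing may stop for a safety reason. The causality judgement that decides whether a later event is still collected is made in an open-label, single-group study with no comparator. The missing-report rule would then turn uncollected time into an apparent absence of the event.

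**Working it through.** **Inputs.** Optimal intervals in Table 5: Visit 1 at 90 days of age, 45 days to Visit 2, 45 days to Visit 3, Visit 5 at 540 days of age, 30 days to Visit 6. The allowed Visit 6 interval comes from the footnote: "An interval of 21-48 days between Visit 3 and Visit 4, and between Visit 5 and Visit 6". The collection limit is last dose + 30 days (8.2.1).

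**Reproducing the plan's own figure.** Visit 6 falls at 540 + 30 = 570 days of age. Time in study is 570 − 90 = 480 days, or 480/30 = 16.0 months. This matches the stated duration of approximately 16 months.

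**All-cause coverage on the optimal schedule for a child who stays to Month 16.** The end of collection is the smaller of (day of last dose + 30) and 480. Uncovered days are 480 minus that.

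| Last dose received | Study day of dose | Collection ends | Uncovered days | Covered |
|---|---|---|---|---|
| Dose 1 | 0 | 0 + 30 = 30 | 480 − 30 = 450 | 30/480 = 6.25% |
| Dose 2 | 45 | 45 + 30 = 75 | 480 − 75 = 405 | 75/480 = 15.6% |
| Dose 3 | 90 | 90 + 30 = 120 | 480 − 120 = 360 | 120/480 = 25.0% |
| Booster | 540 − 90 = 450 | 450 + 30 = 480 | 0 | 100% |

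**Boosted child over the allowed windows.** If Visit 6 is 21 to 30 days after the booster, nothing is uncovered. If it is on Day 48, 48 − 30 = 18 days are uncovered. Over the allowed ages at Visit 1 (90 to 120 days) and Visit 5 (540 to 570 days), coverage with a Day 48 visit runs from 450/468 = 96.2% to 510/528 = 96.6%.

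**Do the narrower streams close the gap?** Not fully. An SAE that is unrelated to the vaccine, to study participation and to any concurrent GSK product, and that does not lead to withdrawal from the study, fits none of them. This includes an unrelated SAE that ends dosing but not participation.

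**Can a site know which rule applies?** Not always. Take an unrelated SAE at Month 8 (about Day 240) in a child who has had three doses. If the booster is later given, collection runs to Day 480 and the event is inside. If it is not, Dose 3 was the last dose, collection closed at Day 120 and the event is outside. Section 6.5 lists an immunodeficient condition as an absolute contraindication. A newly found one could prevent the booster and so place its own SAE outside required collection. Section 8.2.2 calls any event outside the 8.2 reporting period post-study, which could then describe a child still attending visits.

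**Scale across the study (assumption).** The documents give no rate of stopping early while remaining in the study. Suppose the share is between 2% and 15% of 235, about 5 to 35 children. The upper value borrows the non-evaluable allowance in protocol 10.3, which is defined for the immunogenicity analysis, so it only marks the top of the range. The planned follow-up time outside all-cause collection would then be:

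- at 2%: 0.02 × 360/480 = 1.5% (all stop after Dose 3) to 0.02 × 450/480 = 1.9% (all stop after Dose 1)
- at 15%: 0.15 × 360/480 = 11.25% to 0.15 × 450/480 = 14.1%

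**The case against.** A reader might infer that the endpoint cannot be measured at all, or that there is a hole in collection between the primary and booster epochs. The documents support neither. The 30-day limit runs from the last dose, not from each dose, so collection is continuous from Dose 1. For every boosted child it reaches study end on the optimal schedule.

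A reader might also infer that children stopped for safety reasons will appear free of SAEs. That does not follow either:

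- The missing-report rule works per child and per event. An SAE already reported stays counted.
- The post-vaccination reactions in 6.5 that carry a time limit have limits of 48 hours, 3 days or 7 days, well inside the 30-day period.
- Section 8.4.1.1 keeps unresolved SAEs under review to the end of the study.
- Not all early stops are safety stops. Section 9.2.2 allows other reasons and parental decisions. Under 6.5, continuing after a contraindication is at the investigator's discretion.

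The effect on the epoch analyses is also limited. The booster-epoch cohort contains only boosted children, so early stoppers are not in it. A child stopped after Dose 3 is covered to Day 120, the planned end of the primary epoch. All analyses are descriptive, and this is a secondary endpoint. Sites that follow Table 4 may collect the events anyway.

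All of this stands and narrows the point. It does not remove it. After a stop at Dose 1 or Dose 2, 120 − 30 = 90 or 120 − 75 = 45 days of the primary epoch itself are uncovered. The whole-study table claims the full period for all vaccinated children. That sites may follow Table 4 rather than 8.2.1 is the inconsistency, not its solution.

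**Conclusion.** Wrong as written, for a limited group. Protocol 8.2.1 conflicts with Table 4 and with the endpoint in protocol 10.2 and SAP 4.2 for children who stop vaccination and remain in the study. For them, SAEs outside the three continuing streams are not required for about 360 to 450 of 480 days, and the whole-study table reads any such event as not having occurred. For boosted children the discrepancy is 0 to 18 days within the allowed interval and is minor.

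The day counts assume the optimal Table 5 intervals, attendance to Month 16 and no further dose. The number of children affected is unknown and may be small, so the percentages of follow-up time in the working are illustrations, not forecasts. Nothing is inferred from Table 13, because its shading cannot be read in the text available. The point should be corrected, but it does not undermine the SAE endpoint for the study as a whole.

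**What to change.** Change the sentence in protocol 8.2.1 so that SAEs of any cause are collected from the first dose until study conclusion or last contact, for every child still in the study, whether or not dosing has stopped. That agrees with Table 4 and with the endpoint as now worded. Check that Table 13 shows the same period.

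If the sponsor prefers to keep the 30-day limit, restate the endpoint in protocol 10.2, the synopsis and SAP 4.2 as running from Dose 1 to 30 days after the last dose received. Relabel the whole-study SAE table to match, and bring the SAE row of Table 4 into line.

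The first option costs one sentence and a few extra SAE reports. It adds no visits, because Table 4 already schedules SAE recording at each one. The second costs no extra data collection, but gives up all-cause SAE information to study end in the children who stopped early.

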8.2.2. Post-Study adverse events and serious adverse events

A post-study AE/SAE is defined as any event that occurs outside of the AE/SAE reporting period defined in Section 8.2. Investigators are not obligated to actively seek AEs or SAEs in former study participants. However, if the investigator learns of any SAE at any time after a subject has been discharged from the study, and he/she considers the event reasonably related to the investigational vaccine, the investigator will promptly notify the Study Contact for Reporting SAEs.

8.2.3. Evaluation of adverse events and serious adverse events**8.2.3.1. Active questioning to detect adverse events and serious adverse events**

As a consistent method of collecting AEs, the subject's parent(s)/*adoptive parent(s)* should be asked a non-leading question such as:

'Has your child acted differently or felt different in any way since receiving the vaccine or since the last visit?'

When an AE/SAE occurs, it is the responsibility of the investigator to review all documentation (e.g. hospital progress notes, laboratory and diagnostics reports) relative to the event. The investigator will then record all relevant information regarding an AE/SAE in the eCRF. The investigator is not allowed to send photocopies of the subject's medical records to GSK Biologicals instead of appropriately completing the eCRF. However, there may be instances when copies of medical records for certain cases are requested by GSK Biologicals. In this instance, all subject identifiers will be blinded on the copies of the medical records prior to submission to GSK Biologicals.

The investigator will attempt to establish a diagnosis pertaining to the event based on signs, symptoms, and/or other clinical information. In such cases, the diagnosis should be documented as the AE/SAE and not the individual signs/symptoms.

(Amended 11 October 2016)

8.2.3.2. Assessment of adverse events

8.2.3.2.1. Assessment of intensity

The intensity of the following solicited AEs will be assessed as described:

Table 14 Intensity scales for solicited symptoms in infants/toddlers

Infant (below 12 months of age) /Toddler (15–24 months)		
Adverse Event	Intensity grade	Parameter
Pain at injection site	0	None
	1	Mild: Minor reaction to touch
	2	Moderate: Cries/protests on touch
	3	Severe: Cries when limb is moved/spontaneously painful
Redness at injection site		Record greatest surface diameter in mm
Swelling at injection site		Record greatest surface diameter in mm
Increase in limb circumference post-dose 4 (according to where vaccine was administered)		Record the limb circumference at the level of the injection site
Fever*		Record temperature in °C
Irritability/Fussiness	0	Behaviour as usual
	1	Mild: Crying more than usual/no effect on normal activity
	2	Moderate: Crying more than usual/interferes with normal activity
	3	Severe: Crying that cannot be comforted/prevents normal activity
Drowsiness	0	Behaviour as usual
	1	Mild: Drowsiness easily tolerated
	2	Moderate: Drowsiness that interferes with normal activity
	3	Severe: Drowsiness that prevents normal activity
Loss of appetite	0	Appetite as usual
	1	Mild: Eating less than usual/no effect on normal activity
	2	Moderate: Eating less than usual/interferes with normal activity
	3	Severe: Not eating at all

*Fever is defined as temperature $\geq 37.5^{\circ}\text{C}$ for oral, axillary or tympanic route, or $\geq 38.0^{\circ}\text{C}$ for rectal route. The preferred route for recording temperature in this study will be axillary.

Mm = millimetre

The maximum intensity of local injection site redness/swelling will be scored at GSK Biologicals as follows:

0	:	Absent
1	:	≤ 5 mm
2	:	> 5 mm and ≤ 20 mm
3	:	> 20 mm

The maximum intensity of fever will be scored at GSK Biologicals as follows:

Axillary

0	:	< 37.5°C
1	:	≥37.5°C and ≤ 38.0°C
2	:	> 38.0°C and ≤ 39.0°C
3	:	> 39.0°C

Prior to analysis, the increase in limb circumference as compared to the baseline pre-vaccination measurement will be scored for each subject at GSK Biologicals' as follows:

Grade 0 = Increase in limb circumference ≤5 mm

1 = Increase in limb circumference >5 mm but ≤20 mm

2 = Increase in limb circumference >20 mm but ≤40 mm

3 = Increase in limb circumference >40 mm

The investigator will assess the maximum intensity that occurred over the duration of the event for all unsolicited AEs (including SAEs) recorded during the study. The assessment will be based on the investigator's clinical judgement.

For unsolicited symptoms and adverse events associated with large injection site reactions (e.g. induration and functional impairment), the intensity should be assigned to one of the following categories:

The intensity should be assigned to one of the following categories:

1 (mild) = An AE which is easily tolerated by the subject, causing minimal discomfort and not interfering with everyday activities.

2 (moderate) = An AE which is sufficiently discomforting to interfere with normal everyday activities.

3 (severe) = An AE which prevents normal, everyday activities. In a young child, such an AE would, for example, prevent attendance at a day-care centre and would cause the parent(s)/*adoptive parent(s)* to seek medical advice.

(Amended 11 October 2016)

An AE that is assessed as Grade 3 (severe) should not be confused with a SAE. Grade 3 is a category used for rating the intensity of an event; and both AEs and SAEs can be assessed as Grade 3. An event is defined as 'serious' when it meets one of the pre-defined outcomes as described in Section 8.1.2.

